4.6.1 Standardized Radiotherapy

4.6.1.1 External Irradiation (IMRT will not be allowed on this study.)

All participants will receive 41.4-45 Gy external beam RT delivered to the pelvis in 23-25 fractions of 1.8 Gy. Treatments are to be delivered daily, five fractions per week and should be completed within 5 weeks \pm 3 days. Participants should be treated with bladder distention (although this is not mandatory), and bowel exclusion devices (e.g. belly boards) are allowed. If overall treatment time for external pelvic RT exceeds 38 days, the reason for the delay must be documented. If intracavitary RT cannot be performed, shrinking field technique should be performed to bring the gross tumor volume with adequate margins (minimum 1 cm) to a minimum total dose of 65 Gy. An attempt should be made to exclude all small bowel from treatment field after 50.4 Gy.

4.6.1.1.1 Dose Specification

The dose to the pelvis shall be calculated at the intersection of the axes of the 4-field box. The dose to point B shall also be calculated using an off-axis calculation (or identified on the isodose distribution). In patients not undergoing brachytherapy, point B dose will be calculated at the point on pelvic side wall (at the level of superior wall of acetabulum). Heterogeneity corrected dose calculations are not allowed.

The dose to CENTRAL STRUCTURES shall be the sum of the dose at the intersection of the axes of the 4-field box and the dose to point A from the intracavitary treatment. The dose to SIDE WALL STRUCTURES shall be calculated bilaterally (reported separately) and shall be the sum of the dose at the intersection of the axes from the 4-field box plus the intracavitary dose to point B plus the contribution from the parametrial fields. For 2 dimensional planning, the dose at the central axis and pelvic side walls shall not differ by more than 10%. For 3 dimensional planning, the dose range shall be within 95% to 107% of the prescription dose.

Fractionation: Conventional fractionation will consist of one fraction per day, total five fractions per week.

Therapy interruptions: If interruption of radiation should occur for greater than two weeks, the protocol Radiation Oncology Study Chair must be notified.

Dose deviations: A discrepancy in dose (as specified in the protocol) of 6-10% and >10% will be considered as minor and major deviations from the protocol, respectively

4.6.1.2 Intracavitary Brachytherapy

For each participant, institutions will select the dose rate to be used for brachytherapy—either HDR or LDR.

4.6.1.2.1 Low-Dose Rate (LDR) Brachytherapy

Following the completion of whole pelvic RT, the participant will receive 35-43.6 Gy to Point A (Refer to [Appendix VIII](#) Description of points A, B and ICRU Bladder/Rectum) by intracavitary implant with a standard medical radiation source listed on the American Association of Physicists in Medicine (AAPM) source registry (<http://irochouston.mdanderson.org>). The dose table (Refer to [Section 4.6](#)) should be utilized in order to ensure adequate total dose delivery. The participant may receive the LDR

dose in one or two implants at the discretion of the radiation oncologist.

Ideally, external should finish within 35 days and brachytherapy within 3 weeks of completion of whole pelvic RT (WPRT). The first implant should be performed promptly upon completion of WPRT. If external is delayed up to 38 days, and two brachytherapy sessions are planned, the second session shall be completed within 18 days of the completion of WPRT to keep the total RT duration to within 56 days.

4.6.1.2.2 High-Dose Rate (HDR) Brachytherapy

Refer to [Appendix VII](#) (HDR Brachytherapy) for guidelines of vaginal surface dose, normal tissue tolerances, packing and imaging.

4.6.1.2.3 HDR Schema

- Dose to Point A with each HDR brachytherapy fraction: 6 - 9 Gy.
- Number of weekly HDR brachytherapy procedures: no more than four.
- Total HDR brachytherapy dose to Point A: 18-28 Gy.

4.6.1.2.4 Timing

HDR brachytherapy should start by week 4. When HDR brachytherapy begins, at least one implant will be performed per week with no external beam therapy given on the day of the insertion. If the majority of the external beam radiation has been given (>20 fractions), then two implants per week could be done separated by at least 72 hours in order to complete all treatment within eight weeks.

4.6.1.2.5 Doses

Each HDR brachytherapy fraction will give 6-9 Gy/fraction to Point A. (Refer to [Appendix VIII](#) Description of points A, B and ICRU Bladder/Rectum). Each participant may be treated with up to four HDR implants with the HDR total dose ranging from 18-28 Gy (Total HDR dose) that is equivalent to an LDR delivered of 35-43.6 Gy depending on the total external beam dose given (Refer to [Appendix VII](#) HDR Brachytherapy).

4.6.1.2.6 HDR Instruments

It is strongly recommended that tandem and ovoids be used for HDR brachytherapy. However, tandem and rings are considered acceptable. A tandem and cylinder is allowed only for participants where tandem and ovoid application is not possible due to extent of disease.

4.6.1.2.7 Determination of Normal Tissue Tolerance

In order to stay below an LDR equivalent of 70 Gy to the rectum (Biological Equivalent Dose (BED):120 Gy₃) for four HDR implants, including the 45 Gy contribution from the external beam radiation, the rectum should receive less than 4.1-6.1 Gy for each HDR fraction of 6-9 Gy (68% of the prescribed dose to Point A). The dose to the bladder should be less than 4.6-6.9 Gy per each HDR fraction of 6-9 Gy (77% of the prescribed dose to Point A). As in LDR brachytherapy, every attempt should be made to deliver tumoricidal doses, even if the late responding tissues receive a slightly higher dose. (Refer to [Appendix VII](#): HDR Brachytherapy).

4.6.1.3 Parametrial Boost to Involved Parametrium

Participants may receive a parametrial boost at the discretion of the treating radiation oncologist. The radiation oncologist will choose the dose to be used to the involved parametrium based on bulk of parametrial disease at presentation.

The parametrial boost shall be 5.4-9.0 Gy in 3-5 fractions of 1.8 Gy per fraction given AP/PA daily to midplane if unilateral or bilateral parametrial boost is used. The prescription point should be at the center of the unblocked portion of the field. The parametrial boost should be delivered if possible between implant 1 and 2 or immediately after implant 1 if only one implant is used. The total elapsed time for completion of external whole pelvis, intracavitary RT, and parametrial RT shall not exceed 56 days. If a subject who is either in screening or before study entry has received emergency radiation therapy as described in [Section 4.5](#), then definitive radiation therapy should be started as soon as possible so the total treatment time does not exceed 56 days.

4.6.2 Dose Distribution for All Regimens

A four-field box technique with parallel opposed AP/PA and two opposing lateral fields should be used. AP/PA only fields are allowed in thin women but are strongly discouraged and should only be used with 10 MV or higher energy

beams. Dose distribution across clinical target volume shall not vary more than 10% from the recommended dose. All fields must be treated daily.

4.6.3 Radiation Equipment

- 4.6.3.1 Radiation sources must be of megavoltage energy with an SSD of 80 cm or greater. The minimum beam energy allowed on a linear accelerator is 4MV photons. If Cobalt-60 or 4MV is being used, a 4 field box shall be used for patients with a separation of >18 cm. The peak infield dose should not exceed the dose at the isocenter by more than 10%. All participants will undergo simulation for localization and verification of external RT treatment portals. CT scan with contrast is required in pre-treatment planning. If the participating site cannot perform CT simulation and yet has 3D treatment planning software, a diagnostic CT scan with contrast shall be available for treatment planning purposes. Orthogonal films shall be performed for each implant. Intracavitary treatment will be delivered with standard applicators. Interstitial brachytherapy is not permitted on this trial. If it is felt to be clinically imperative to deliver interstitial brachytherapy, it will be considered a major treatment deviation.
- 4.6.3.2 Intracavitary RT may be delivered by cesium-137 or equivalent radiation source for LDR brachytherapy or cobalt-60 or iridium-192 for HDR brachytherapy in standard or commonly used tandem and ovoid applicators. Only the medical radiation brachytherapy sources listed on the AAPM source registry (<http://irochouston.mdanderson.org>) may be used.

4.6.4 External Radiation Fields (Refer to [Appendix IX](#) Blank Diagram Anterior and [Appendix X](#) Blank Diagram Lateral)

4.6.4.1 Whole Pelvis Field

The external RT target volume shall encompass, with adequate margins, the primary cervical tumor and its gross extension and any grossly involved pelvic lymph nodes as well as possible microscopic extension to pelvic lymph nodes and the uterus.

The use of IMRT will not be allowed on this study.

4.6.4.2 AP/PA pelvic fields

The superior border will be through the L4-5 interspace unless the target volume (e.g. involved iliac lymph nodes or local disease) would not be encompassed adequately in a cephalad direction. In the latter case, a 2 cm margin should be added to the highest level of pathologic abnormality, but should not be cephalad to the L-3/L-4 interspace. The

lateral border will be 2 cm beyond the lateral margins of the bony pelvis. The inferior border will be inferior to the obturator foramen or the lowest extension of disease with at least a 3 cm margin. The inferior extent of cervical cancer or vaginal extension should be marked so that the inferior border of disease can be documented. Uninvolved normal tissues may be blocked although the position of the uterus should be drawn on at least one anterior and lateral field to ensure adequate coverage by transfer of the volume from imaging of the pelvis onto the simulation films. Any bulky adenopathy in the pelvis from imaging scans should be documented on the simulation films as well.

4.6.4.3 Lateral Pelvis Fields

The anterior border should be a horizontal line drawn just anterior to the symphysis pubis, and the posterior border a horizontal line at the posterior border of the sacrum. Superior and inferior borders will be the same as for the anterior and posterior fields. If clips are present from the lymph node dissection to document the position of the lymph nodes, then these should be used as a guide when anterior blocks are designed to shield small bowel. At least 3 cm should not be blocked anterior to the L-5 vertebral body. Also the anterior two-thirds of the L-5 vertebral body should not be blocked.

Posterior blocking should be designed such that gross disease is encompassed with at least a 2 cm margin. The outer table of the sacrum should be blocked to protect the sacral plexus on lateral fields.

4.6.4.4 Parametrial Boost Fields

The superior border should be reduced to include only the true pelvis. The upper border of the true pelvis field is defined as 1 cm above the inferior aspect of the sacroiliac joint (Refer to [Appendix VIII](#) Description of ICRU Bladder/Rectal Dose Reporting Points). Parametrial block should be a minimum of 4-5 cm wide if bilateral parametrial boost is used and may be shaped to the point A isodose. Unilateral parametrial boost would be used if only unilateral involvement was noted (Refer to [Section 4.6.1.3](#)).

4.6.5 Simulation and portal films should be available to the AMC for auditing purposes along with the participant records for the whole pelvic RT fields and parametrial boost. Orthogonal AP and lateral simulation films will be taken following each intracavitary insertion. The orthogonal films and calculations of the intracavitary insertion shall also be made available for auditing purposes for the AMC along with the participant records. Copies of the CT, MRI or other relevant scans, if performed, documenting the relevant tumor volume shall be made available as well.

4.6.6 Radiation Therapy Quality Control and Documentation

The Imaging and Radiation Oncology Core Houston QA Center (IROC Houston QA Center), a National Cancer Institute funded organization with guidance from the AAPM, will supervise the dosimetry control for this clinical trial. To participate in the trial, the institution must demonstrate the ability to achieve an accuracy of $\pm 5\%$ in measuring calibrated reference beam output of their external beam therapy units on an annual basis. Each participant record will be reviewed by the IROC Houston QA Center to verify that each participant received their radiation therapy dose to within $\pm 5\%$ for delivering the external beam prescribed dose and $\pm 15\%$ for the brachytherapy boost.

The radiation therapy quality assurance process is described in [Appendix XII](#).

4.6.7 Expected Toxicity

Gastrointestinal: Nausea and vomiting may occur, especially after the first few treatments. It is recommended that participants be pretreated with anti-emetics before each daily treatment. The use of antiemetics, like any prescribed concomitant medications, will require documentation. Intractable nausea and vomiting beyond the first few days should arouse suspicion of recurrent tumor or other causes of bowel obstruction, as it is rarely seen as a result of radiation alone. Increased bowel activity with diarrhea can be expected fairly routinely after the first two weeks of pelvic radiation. It is recommended that instructions be given to participants for a low fiber, low fat, and bland diet. Most participants will require antidiarrheal medications during therapy.

Should GI toxicity become severe enough to require hospitalization for IV fluid replacement, treatment should be discontinued temporarily until the participant's condition improves. Study Chairs must be notified and documentation of appropriate use of antiemetics may be requested.

Radiation therapy to the pelvis with the concomitant use of chemotherapy on this protocol may enhance the expected toxicity from radiation therapy alone. The expected adverse effects and the guidelines for treatment modifications are described in [Section 6.0](#).

4.6.8 General Radiation Schedule

Radiation therapy (RT) Schedule (with low-dose or high-dose rate):

Day Number	
Day 1	Start whole pelvic radiation therapy (WPRT)
Approximately Day 35	Complete WPRT
After Day 35	Start brachytherapy and deliver parametrial boosts, if prescribed*
Day 50, but no later than Day 56	Complete all radiation therapy*

***If a subject who is either in screening or in the pre-screening period has received emergency radiation therapy, then definitive radiation therapy should be started as soon as possible so the total treatment time does not exceed 56 days.**

*Parametrial boost not required in Stage IB2 and IIA participants. Number of fractions left to the discretion of physician.

4.7 Duration of Study

Each participant should complete the study treatment unless disease progression occurs or toxicity prohibits further therapy. Regardless of whether the treatment is completed, the participant should be followed at least at month 6 and month 12 after the completion of treatment.

Participants should be contacted by clinic staff by appropriate communication mechanisms in order to encourage and maintain the participant's follow-up with their study visits. Follow-up mechanisms may be done by phone, text, email or reminder cards. If a participant is unable or unwilling to come to the clinic for a follow-up visit, clinic staff may obtain information regarding the patient's general health, adverse events, medication changes, or other appropriate changes verbally or via an email or text message from the participant. This information must also be documented within the participant's medical record by a note or copy of the email, phone call, or text message.

5.0 CLINICAL AND LABORATORY EVALUATIONS

5.1 Screening Evaluations

The following will be obtained within the time frames specified in [Appendix I](#):

5.1.1 Within 28 days prior to initiating protocol therapy

- Medical history for eligibility
- Physical examination including: weight and height for BSA calculation, performance status (Refer to [Appendix II](#)), general physical exam, and pelvic exam if judged as necessary by the investigator.
- Tumor measurements and clinical staging
- CT scan with contrast of pelvis and abdomen
- Chest X-ray
- CD4+ T-cell count
- HIV viral load

5.1.2 Within 14 days prior to initiating protocol therapy

- CBC and differential
- Calculated creatinine clearance
- SGOT, SGPT, alkaline phosphatase, bilirubin
- Electrolytes (sodium, potassium, chloride, magnesium)
- Pregnancy test (serum or urine)
- Review of interim medical history including concomitant medications
- Slides for central pathology review--formalin-fixed tissue H&E and unstained slides from original cancer biopsy tissues (refer to [Appendix IV](#))
- Optional: Cytoscopy per local standard of care for clinical staging
- Optional: Intravenous pyelogram (IVP) per local standard of care for clinical staging
- Anal and cervical swabs to evaluate the exploratory study objectives (refer to [Appendix XI](#))
- Serum to evaluate the exploratory study objectives (refer to [Appendix XI](#))

5.2 Evaluations during Chemo-Radiation Treatment

5.2.1 Weekly During Chemo-Radiation (Day 1, 8, 15, 22, 29, 36, (- 2 days))

The following laboratory results will be obtained on the same day or up to 2 days prior to cisplatin administration unless otherwise noted:

- CBC and differential
- Calculated creatinine clearance
- Electrolytes (sodium, potassium, chloride, magnesium)
- Review of interim medical history including concomitant medications and adverse events
- ART adherence assessment will be collected on Day 8, Day 15, Day 22, Day 29, and Day 36.

- Physical Examination on Day 22 prior to treatment.

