4.2.2 Chemotherapy

Cisplatin 40 mg/m² IV over 30-60 minutes given weekly on days 1, 8, 15, 22, 29 and 36 for a total of 6 weekly cycles.

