5.2.2 Assessments at the Time of Chemo-Radiation Therapy Completion

The following assessments must be completed within 7 days of chemo-radiation therapy completion unless otherwise specified. These assessments are required for all participants regardless of the reason for treatment discontinuation (e.g. treatment completion or early discontinuation).

- Review of interim medical history including concomitant medications and adverse events.
- ART adherence assessment.
- Physical examination.

The following assessments must be completed either on the final day of chemo-radiation therapy or within 4 weeks after the final dose of chemo-radiation therapy:

- Anal and cervical swabs to evaluate the exploratory study objectives (refer to [Appendix XI](#)).
- Serum to evaluate the exploratory study objectives (refer to [Appendix XI](#)).

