6.1.1.1 Blood/Bone Marrow (Hematologic)

Hematologic toxicity is seen infrequently unless pelvic radiation is accompanied by chemotherapy. A CBC should be obtained weekly, and if the ANC falls below $1500/\text{mm}^3$ ($1.5 \times 10^9/\text{L}$) or the platelet count drops below $100,000/\text{mm}^3$ ($100.0 \times 10^9/\text{L}$), counts should be obtained twice weekly. Treatment may proceed if $\text{ANC} > 1000/\text{mm}^3$ ($1.0 \times 10^9/\text{L}$), and platelet count $> 50,000/\text{mm}^3$ ($50.0 \times 10^9/\text{L}$).

Every effort should be made to maintain hemoglobin $\geq 10\text{g/dL}$ (6.2 mmol/L). It is up to the individual investigator's discretion as to how best to achieve this.

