6.2.2 Definition of Dose-Limiting Toxicity for Cisplatin

Dose-limiting non-hematologic toxicities for cisplatin are defined as any grade 3 or worse peripheral neuropathy or ototoxicity OR any grade 4 GI toxicity that are at least possibly related to cisplatin. Dose-limiting hematologic toxicities for cisplatin are defined as any grade 4 anemia, thrombocytopenia, or neutropenia that are at least possibly related to cisplatin.

- 1) If no patient out of the initial three on this dose level exhibits a DLT, then escalate to dose level 0.
- 2) If one patient out of the initial three patients on a dose level exhibits a DLT, then up to three additional patients will be added. If a second patient develops a DLT, even if it is before there are six total patients on that level, then the MTD has been exceeded and no additional patients should be added to this or any higher doses. Thus, the MTD is defined as the highest dose level at which $\leq 1/6$ patients have a DLT. If ≥ 2 patients on a dose level experience a DLT, then the MTD will have been exceeded and no additional patients will be added at that dose level or any higher level.

If dose-limiting toxicity occurs at dose level -2, cisplatin will be discontinued for the remainder of the treatment with radiation therapy alone. The protocol team will review the toxicity and frequency of dose reductions of subjects enrolled in this safety run-in. If the protocol team determines that there is unacceptable toxicity and frequent dose reductions at the 40 mg/m^2 dose in enrolled subjects with a CD4 count $\leq 200/\text{mm}^3$ ($0.2 \times 10^9/\text{L}$), the protocol team will consider reducing the dose for all enrolled subjects with low CD4 counts to dose level -1 or dose level -2 for the remainder of the trial.

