APPENDIX I: SCHEDULE OF EVENTS

The following observations and tests are to be performed and recorded on the appropriate form(s):

Tests and Observations	Prior to Entry	Weekly During Chemo-Radiation	Chemo-Radiation Therapy Completion or Premature Treatment Discontinuation ¹⁰	3, 6, 9, and 12 Month Follow-up	After Diagnosis of Recurrence	Premature Study Discontinuation ⁶
Medical History	X ¹					
Physical exam	X ¹	X ²	X ²	X ²		X
Tumor measurements and clinical staging	X ¹					
CT scan with contrast of pelvis and abdomen	X ¹			X ³	X	X
Chest X-ray †	X ¹				X	X ⁷
CD4+ T-cell count	X ¹			X ⁴	X	X ⁷
HIV viral load	X ¹			X ⁴	X	X ⁷
CBC + differential	X ⁵	X				X ⁷
Calculated creatinine clearance	X ⁵	X				X ⁷
SGOT, SGPT, alkaline phosphatase, bilirubin	X ⁵					X ⁷
Electrolytes (Na, K, Cl, Mg)	X ⁵	X				
Serum or urine pregnancy test *	X ⁵					X ⁸
Review of interim medical history		X	X	X ⁸	X	X
Slides for central pathology review	X ⁵					
ART Adherence		X	X	X		
Cytoscopy, IVP	X ^{5,+}					
Anal and cervical swabs for HPV-associated disease research	X ⁵		X ⁹			X
Serum for HPV-serology	X ⁵		X ⁹		X	X

X¹ Must be obtained within 28 days prior to initiating protocol therapy

X² At day 22 prior to treatment, at treatment discontinuation, and every 3 months for 1 year.

X³ CT with contrast of abdomen and pelvis to be done prior to study entry, 6 months +/- 4 weeks and 12 months +/- 4 weeks after concomitant chemoradiotherapy. Can perform CT without contrast only if recent creatinine ≥ 1.5 mg/dL (within 4 weeks of scan).

X⁴ Every 6 months while on protocol

X⁵ Must be obtained within 14 days prior to initiating protocol therapy. If ANC $\leq 1,500/\text{mm}^3$ ($1.5 \times 10^9/\text{L}$) or platelets $\leq 50,000/\text{mm}^3$ ($50 \times 10^9/\text{L}$), repeat twice per week until over these values or subject off trial.

X⁶ Evaluations should be performed whenever possible, preferably at the time of or up to 1 month after withdrawal from study.

- X⁷ Tests are required if not done within the last 3 months.
- X⁸ Every 3 months for 1 year.
- X⁹ Anal and cervical swabs and serum for HPV-associated disease research will be collected on the final day of chemo-radiation therapy or within 4 weeks following the final chemo-radiation therapy.
- X¹⁰ Assessments must be completed within 7 days of the completion of chemo-radiation therapy. This visit is required for all participants and refers to both to scheduled completion of treatment and premature treatment discontinuation

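### The evaluation schedule lists no blood count, creatinine or electrolytes after the Day 36 pre-dose draw, and the protocol's sections disagree on whether these tests continue to the end of radiation

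*Combined protocol and SAP*

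**What the plan says.** **During treatment.** Section 5.2.1 is headed "Weekly During Chemo-Radiation (Day 1, 8, 15, 22, 29, 36, (- 2 days". It lists a blood count with differential, calculated creatinine clearance and electrolytes, each "obtained on the same day or up to 2 days prior to cisplatin administration". Section 4.2.2 has cisplatin "given weekly on days 1, 8, 15, 22, 29 and 36 for a total of 6 weekly cycles".

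**End of radiation.** Section 4.6.8 gives completion of all radiation as "Day 50, but no later than Day 56".

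**Completion visit.** Section 5.2.2 states: "The following assessments must be completed within 7 days of chemo-radiation therapy completion unless otherwise specified". The list that follows is interim history with adverse events, ART adherence and physical examination, plus swabs and research serum on a wider window. None of the three safety tests appears.

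**Follow-up.** Sections 5.3.1 to 5.3.4 (months 3, 6, 9 and 12) also omit them. In Appendix I the three rows carry no mark in the completion or follow-up columns.

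**Radiation section.** Section 6.1.1.1 says: "A CBC should be obtained weekly, and if the ANC falls below" a stated limit, or platelets do, counts become twice weekly. It names no last day. Section 6.1.2.1 adds twice-weekly counts while external radiation is delayed for low counts.

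**Use of the results.** Safety and tolerability is a primary objective (2.2.2). Section 6.2.2 states: "Dose-limiting hematologic toxicities for cisplatin are defined as any grade 4 anemia, thrombocytopenia, or neutropenia that are at least possibly related to cisplatin". Section 11.1 tabulates adverse events by grade, and 11.4 names blood/bone marrow as one of five analyzed categories.

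**The concern.** Grade 4 anemia, neutropenia and thrombocytopenia are graded from a blood count, and a rise in creatinine or an electrolyte disturbance can be silent. The protocol expects such effects: 4.3.1.3 lists nephrotoxicity and electrolyte imbalance for cisplatin, and 4.2.3.2 warns that tenofovir may worsen renal insufficiency. If the last scheduled sample precedes the last dose, a later laboratory event is found only if a clinician happens to order a test.

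Two outputs depend on this. One is the set of safety tables for a primary objective. The other is the run-in for women with CD4 at or below 200, where three women decide the next step and a single dose-limiting event changes it. Because the sections differ, ascertainment could also vary by site according to which section its staff follow.

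**Working it through.** The plan states no figure for this point, so the check is calendar arithmetic followed by a comparison of sections.

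**Inputs.** Last listed draw: Day 36, or Day 34 with the two-day window (5.2.1). Sixth dose: Day 36 (4.2.2). End of radiation: Day 50 to Day 56 (4.6.8). Completion visit: within 7 days of completion (5.2.2). Enrollment: 45 women (3.3).

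**Step 1. Time without a listed draw** = end of radiation minus last listed draw.
- From Day 36: 50 − 36 = 14 days; 56 − 36 = 20 days.
- From Day 34: 50 − 34 = 16 days; 56 − 34 = 22 days.
- Share of the course, from Day 36: 14/50 = 28%; 20/56 = 36%.

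**Step 2. Which doses have a later draw.** For doses one to five, the next pre-dose draw (Day 8, 15, 22, 29 or 36) also serves as a post-dose measurement. Dose six has no next draw. If dose six is moved into brachytherapy, as 6.2.6 allows, its pre-dose draw moves with it and the interval in Step 1 shortens, but there is still no listed draw after the dose.

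**Step 3. Sections side by side, for a woman who completes the study.**

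| Place | Blood count after Day 36 | Creatinine and electrolytes after Day 36 |
|---|---|---|
| 5.2.1 | Not listed | Not listed |
| 5.2.2 and 5.3.1 to 5.3.4 | Not listed | Not listed |
| 6.1.1.1 | Weekly, no end day | Not mentioned |
| Appendix I, weekly column | Marked, no days given | Marked, no days given |
| Appendix I, completion and follow-up columns | No mark | No mark |

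For blood counts the documents conflict. For creatinine and electrolytes, only the undated column heading in Appendix I could extend the draws. No post-treatment draw is listed for any of the three. Footnote 3 of Appendix I makes omission of CT contrast depend on a recent creatinine, but schedules none.

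**Step 4. If 6.1.1.1 governs.** Weekly counts carried on from Day 36 fall on Day 43 and Day 50, so the longest interval without a count before the end of radiation is about 7 days. Section 6.1.1.1 changes nothing for creatinine and electrolytes, which stay at 14 to 20 days.

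**Step 5. Run-in.** Under 6.2.2, no dose-limiting event in three women leads to escalation to dose level 0; one event leads to up to three more women at the same level. One true event that goes undetected turns 1/3 into 0/3 and moves the decision from the second branch to the first.

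**Step 6. What a completion sample would reach.** The visit falls between Day 50 and Day 56 + 7 = Day 63, which is 50 − 36 = 14 to 63 − 36 = 27 days after dose six.

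**The case against.** The strongest reply is that the monitoring is there if the protocol is read as a whole. Section 6.1.1.1 requires weekly counts during radiation with no stop day. Appendix I marks all three tests in a weekly column without days, which can be read as running to the last fraction. Adverse-event review and physical examination take place within 7 days of completion and every 3 months for a year, so gastrointestinal, genitourinary, skin and neurologic toxicity is collected. Section 9.1.4 evaluates safety through dose delays, reductions, missed doses and compliance, and no planned cisplatin dose follows the sixth. The dose-limiting definition also covers neuropathy, ototoxicity and gastrointestinal events, and the run-in review already waits until all three women finish or stop treatment.

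Much of this stands. It rules out reading the plan as leaving late toxicity unmeasured: the gap is confined to laboratory toxicity, and for blood counts it is a conflict between sections, not a silence. It does not remove the point. The undated Appendix I column carries the same title as 5.2.1, which does give days, so a site may reasonably take the table as a summary of that section. Nothing in 6.1.1.1 covers creatinine or electrolytes. No place lists a post-treatment sample for completers. Section 9.1.4 is not the whole safety analysis either, since 11.1 and 11.4 tabulate graded events. And waiting for treatment to finish helps the run-in review only if a sample has been taken.

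Three further inferences are tempting but not supported:
- *Drop-outs are tested and completers are not.* Section 5.5 orders these tests only if none was done in the preceding 3 months, and where possible. A woman who leaves during or soon after treatment would usually trigger none.
- *One sixth of laboratory events is lost, because one dose in six has no later draw.* That assumes equal risk per dose and that 6.1.1.1 is ignored. The documents give no rates per cycle.
- *The triggers for twice-weekly counts contradict each other.* The Appendix I wording ("repeat twice per week until over these values or subject off trial") belongs to a footnote attached to the pre-entry mark, while 6.1.1.1 applies during radiation. Different time points are a plausible reading, although the closing words leave some ambiguity.

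**Conclusion.** The point holds as a gap and inconsistency in laboratory ascertainment. On the 5.2.1 day list, women who complete the study have no scheduled blood count, creatinine or electrolytes after the sixth dose, including the last 14 to 20 days of radiation. This rests on treatment being given on schedule and on sites following 5.2.1; for blood counts it disappears largely during radiation if they follow 6.1.1.1.

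The likely direction is fewer laboratory events detected, in the graded safety tables and in the run-in. How many cannot be computed from the documents. A reader might go further and conclude that the run-in decision is biased. The documents show only that one missed event would be enough to change it, not that one is likely. The correction should be made because it is cheap and serves a primary objective.

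**What to change.** 1. Reconcile 5.2.1, 5.2.2, 6.1.1.1 and Appendix I on how long blood counts, creatinine clearance and electrolytes continue, and give the days in Appendix I. The monitoring frequency during radiation is for the sponsor to decide.
2. Add the three tests to the 5.2.2 completion visit as safety-endpoint data. That section already applies to every woman, whatever her reason for stopping, and already calls for a serum sample.
3. State in 6.2.1 that the run-in toxicity review includes those results for all three women.

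The completion sample does not close the gap alone: taken 14 to 27 days after dose six, it would miss an abnormality that had already recovered. Item 1 is therefore still needed.

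**Cost.** Protocol wording, and one routine sample per woman at an existing visit: 1 × 45 = 45 samples. If the reconciled schedule turned out to be weekly to the end of radiation, Days 43 and 50 would add 2 × 45 = 90, for 135 in all. Reported laboratory toxicity rates may come out slightly higher, because more events would be seen.
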